17.8.4 Myocarditis

17.8.4.1 Definition of Myocarditis

Clinical criteria - symptoms of chest pain, arrhythmia or development of HF (as defined above) associated with elevated troponin and ECG changes in the absence of hemodynamically significant CAD* (defined as a stenosis greater than 50% in a major epicardial coronary artery) within the previous 90 days. Typically, this presentation is associated with the presence of – or with a history of a recent - viral infection.

In some situations, the diagnosis might be confirmed by one of the following:

- CMR diagnosis: (Lake Louise II Criteria) **OR**
- Endomyocardial biopsy (if clinically indicated), showing either cellular inflammation and/or immunohistochemistry consistent with inflammation

*thorough evaluation of ischemia by coronary angiography, CT angiography and/or stress test; imaging is at the discretion of the PI but may not be feasible in the presence of COVID-19.

17.8.5 New sustained or symptomatic Arrhythmia

The development of any of the following arrhythmias are considered significant for the patients in this study. The rhythm must be documented by ECG or monitor strip.

- Sinus bradycardia – persistent HR less than 50/minute
- Atrio-ventricular Block – Mobitz Type I
 - Mobitz Type II
 - Complete AV block
- Atrial tachycardia – regular tachycardia with visible P waves sustained for more than 30 seconds. This may be paroxysmal (PAT) or become sustained
- Atrial flutter – atrial rate of 200 – 400 /min
- Atrial fibrillation (AF) – irregularly irregular narrow QRS complex arrhythmia
 - Paroxysmal AF – episode of AF lasting at least 30 seconds
 - Persistent AF: – with uncontrolled ventricular response (>100 beats/min)
 - with controlled ventricular response (<100 beats/min)
- Ventricular Premature Complexes
 - Monomorphic >10 /min
 - Polymorphic >10 /min
- Ventricular Tachycardia with HR greater than 100/min
- Ventricular fibrillation
- Ventricular asystole –cardiac standstill

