Arrhythmias are also common with atrial fibrillation being most prevalent. The pathogenesis is not clear but it is interesting that, in general, inflammation of the left atrial tissue is believed to be the common substrate for this arrhythmia. Ventricular arrhythmias also occur with resultant sudden death (P. P. Liu et al. 2020). In some cases, this has been a complication of concomitant therapy – particularly with Chloroquine or Hydroxychloroquine – both of which may prolong the QT interval. However, in a recent study from Northern Italy, investigators found that even out-of-hospital cardiac arrest was twice as common during a six-week period during the 2020 pandemic, compared to a similar period in 2019 (Baldi et al. 2020).

Finally, several recent reports highlight the high incidence of acute renal failure in patients with COVID-19 – particularly in those ill enough to require ICU management (Richardson et al. 2020). Many of these patients require replacement therapy with dialysis and have a poor prognosis. Indeed, recent Centers for Medicare and Medicaid Services (CMS) data suggest that 50% of patients hospitalized with COVID-19 had chronic kidney disease (“CMS Medicare Claims and Encounter Data” 2020).

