Because of this concern, an electrocardiogram (ECG) will be recorded every other day for the first 7 days of drug dosing and on Days 14, 21 and 28; the recording should be done 5 hours after the morning dose of the study drug (time window 3.5 – 6 hours). The ECG will be assessed by the Investigator at the clinical site, the QT interval measured (the QTc calculated) and recorded in the case report form (CRF), with a copy of the ECG appended. The QT interval is measured from the beginning of the QRS complex to the end of the T wave and averaged over three cardiac cycles. The average QT interval should be corrected for heart rate variability using Bazett's formula ($QT_c = QT / \sqrt{RR}$) or Fridericia's formula ($QT_c = QT / RR^{1/3}$) to create the QTc interval. Each patient should have the QTc measured using the same method on all designated days in the study. If the QTc interval increases to 500 msec or more – or increases 60 msec or more from the baseline recording on any one measurement, this will be reported as an SAE and the study medication will be discontinued.

The QT interval can be obtained from the automated measurements of the ECG recorder, unless the data quality is poor. It is the corrected value that is to be recorded in the CRF.

After 100 patients have completed the Day 28 assessment (or terminated the study earlier), the QTc data will be analyzed (unblinded) by the DSMC. If an impact on the QTc interval by the study drug has been found, the DSMC will evaluate the appropriateness of continuing the trial.

The presence of a bundle branch block represents a particular challenge in properly measuring the QTc interval. Following international recommendations, QT interval should be measured in leads showing the longest QT interval, which is usually in right precordial leads. In presence of a BBB, these leads are strongest affected by conduction delay and therefore hamper adequate measurement. A new formula for evaluation of the QT interval in patients with left bundle branch block (LBBB) was introduced in 2014:

$$QT_{mean} = QT_{BBB} - 50\% QRS_{BBB} \text{ (Bogossian et al. 2014)}$$

This formula has proved to be a reliable tool in clinical practice for QTc interval evaluation in patients with LBBB, right bundle branch block (RBBB) or bifascicular block. (Bogossian et al. 2020; Erkacic et al. 2020)

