10 CRITERIA FOR EVALUATION OF STUDY RESULTS

10.1 Criteria for Evaluation of Efficacy

10.1.1 Primary efficacy outcome

The primary efficacy outcome is the percentage of patients who experience one of the following events during the first 28 days:

- All-cause mortality
- Requirement for ICU admission and/or ventilatory support due to COVID-19
- CV complications*:
 - HF or
 - AMI or
 - myocarditis or
 - new sustained or symptomatic arrhythmia or
 - stroke

*see definitions in Appendix 17.8

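### Read literally, the arrhythmia definition leaves out new atrial fibrillation conducted with bundle branch block: a minor wording defect in the primary composite

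*Protocol*

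**What the plan says.** The primary composite includes "new sustained or symptomatic arrhythmia or" further cardiovascular events within 28 days (Protocol 10.1.1). The Protocol endpoint text and SAP 4.1.2 and 9.1 all send the reader to Protocol Appendix 17.8 for definitions.

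Appendix 17.8.5 opens: "The development of any of the following arrhythmias are considered significant for the patients in this study". It then enumerates rhythms, with no line for other arrhythmias. The lines that matter here are:

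- AF, described as an "irregularly irregular narrow QRS complex arrhythmia", with a paroxysmal sub-type ("episode of AF lasting at least 30 seconds") and a persistent sub-type with controlled or uncontrolled ventricular response.
- Atrial tachycardia, described as "regular tachycardia with visible P waves sustained for more than 30 seconds".
- Atrial flutter, defined by atrial rate.
- "Ventricular Tachycardia with HR greater than 100/min", the only tachycardia line that a wide-QRS rhythm would naturally fall under, apart from fibrillation of the ventricles.

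Bundle branch block is not an exclusion criterion. The QTc exclusion (5.3) and the permanent-suspension rule (6.7.1) both refer to a bundle branch block correction, and Protocol 9.2.3 explains why: "The presence of a bundle branch block represents a particular challenge in properly measuring the QTc interval".

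**The concern.** The AF line makes a feature of ventricular conduction part of the description of an atrial rhythm. A patient with bundle branch block who develops sustained AF has an irregular wide-QRS rhythm. Taken word for word, that rhythm matches neither the AF line nor any other supraventricular line. At a controlled rate it has no line at all. Above 100 beats per minute it could enter only through the ventricular tachycardia line, which would be a wrong diagnosis.

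The rest of the entry suggests that AF was meant to be captured broadly, since it accepts episodes of 30 seconds and both controlled and uncontrolled ventricular response. Protocol 3.4 also gives AF weight: "Arrhythmias are also common with atrial fibrillation being most prevalent". At stake are a few true events in the arrhythmia component, and consistent adjudication if some readers treat the qualifier as binding and others as descriptive.

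**Working it through.** **1. Does anything in the documents relax the wording?**

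- The infarction definition (Appendix 17.8.3.1) lets adjudicators accept an event that misses the strict definition when biomarker or ECG results are unavailable. Appendix 17.8.5 has no such clause.
- The AF sub-types take their meaning from the parent line and say nothing about QRS width.
- Adjudication follows pre-specified definitions in an Event Classification Manual (Protocol 12.6, SAP 4.3). That manual is not among the documents.

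Nothing available widens the AF line.

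**2. The plan's own sample size.** Inputs from Protocol 11.1: placebo 19%, active 9.5%, two-sided alpha 0.05, 80% power. With pooled variance and no continuity correction:

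n per group = [1.96·√(2·0.1425·0.8575) + 0.8416·√(0.19·0.81 + 0.095·0.905)]² / 0.095²
= (0.969 + 0.412)² / 0.009025 ≈ 211.4

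This rounds up to 212, against 211 stated, so the plan's figure reproduces. Power at 211 per group is 79.9% by the normal approximation and 76.8% for the planned Fisher test computed exactly. That gap is a separate matter; 76.8% is the starting point below.

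**3. Number of patients.** The documents give no rate, so these are assumptions: new AF in 3% to 8% of patients, bundle branch block or paced rhythm in 5% to 15%, the two independent, and the same rates in both arms.

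- Low end: 0.03 × 0.05 = 0.0015, and 0.0015 × 422 = 0.6 patients.
- High end: 0.08 × 0.15 = 0.012, and 0.012 × 422 = 5.1 patients.

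This treats every uncounted AF as the patient's only primary event. Given these rates it is therefore an upper bound, because overlap with other components reduces it.

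**4. Power in the protocol as designed.** Take d points off the placebo rate and half that off the active rate, so that the 50% relative reduction is kept. Fisher power is exact, two-sided, at 211 per group.

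| d (points) | Placebo | Active | Overall rate | Fisher power |
|---|---|---|---|---|
| 0 | 19.0% | 9.5% | 14.25% | 76.8% |
| 0.15 | 18.85% | 9.425% | 14.14% | 76.4% |
| 0.5 | 18.5% | 9.25% | 13.88% | 75.4% |
| 1.0 | 18.0% | 9.0% | 13.5% | 74.0% |
| 1.2 | 17.8% | 8.9% | 13.35% | 73.4% |

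The loss is 0.4 percentage points of power at d = 0.15 and 2.8 at d = 1.0. The last row takes the top of the assumed range with no overlap at all and costs 3.4.

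**5. What the current SAP does with the composite.** Patients meeting any part of it are listed without analysis (SAP 9.1.1), and the 60-day version is also only listed (SAP 9.3.1). No subgroups are explored (SAP 6.4.2).

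**The case against.** The strongest reply is that the line is headed by a diagnosis and the words after it are a gloss. Other entries are plainly descriptive, such as the one that explains asystole as cardiac standstill. At least three clinicians verify every endpoint, and nothing says that they would reject documented AF because the QRS is wide. The unseen manual may also already settle the matter. This shows that the literal reading may not be the one applied. It does not remove the defect, because the written rule and a sensible reading of it differ and the documents do not say which governs.

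A reader might infer that these patients are lost to the primary endpoint. The documents do not support that. They fail one component only, and the others remain open. Ventilatory support under Appendix 17.8.1 is a wide route, since it includes new or recurrent oxygen by mask or cannula with saturation below 94%.

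A reader might also expect serious damage to power. Protocol 11.1 already provides for a low rate: if the blinded overall rate is below 14.25%, the sample size is to be increased to preserve 80% power. Every row with a loss in the table falls below that threshold. SAP 6.1 has since dropped the re-estimation because the study ended early, but the power argument has lapsed with it, as the composite is no longer tested.

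It is tempting to add that the loss falls mainly on the cardiovascular disease and heart failure subgroups. The documents give no figures on conduction disease by subgroup.

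Finally, sustained regular supraventricular tachycardia without visible P waves might be called a second omission. The list is the sponsor's selection of rhythms considered significant, and no frequency is available even as an assumption. Adding a category would widen the endpoint, which is the sponsor's choice. Only a clarification can fairly be asked for.

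**Conclusion.** The point holds as a minor defect of wording. As written, Appendix 17.8.5 does not count new AF conducted with bundle branch block towards the arrhythmia component, although such patients are eligible and no latitude clause applies.

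The size rests on assumed rates, with independence and no overlap: at most about 1 to 5 of 422 patients. In the protocol as designed, that costs between less than half a percentage point and about three points of Fisher power. The arm comparison is not biased: the definition is the same in both arms, endpoints are judged in a double-blind trial, and the proportional loss assumed here leaves the relative reduction at 50%. Under the current SAP the only consequence is which patients appear in the composite listings of 9.1.1 and 9.3.1.

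**What to change.** In Appendix 17.8.5, delete the three words that require a narrow QRS complex from the AF line, so that AF documented by ECG or monitor strip counts at any QRS width. Check the Event Classification Manual and bring it into line before unblinding; SAP section 2 says the plan is approved before the blind is broken, so the clarification can be made without knowledge of treatment. Use the same definition for the listings in SAP 9.1.1 and 9.3.1.

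For atrial tachycardia, ask the sponsor only to state whether visible P waves are required or descriptive.

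The cost is three words in the appendix, a matching check of the manual, and possibly a few more rhythm strips to adjudicate.

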17.8.6 Stroke

17.8.6.1 Ischemic Stroke

Stroke is defined as an acute episode of focal or global neurological dysfunction caused by brain, spinal cord, or retinal vascular injury as a result of hemorrhage or infarction.

Hemorrhage may be a consequence of ischemic stroke. In this situation, the stroke is an ischemic stroke with hemorrhagic transformation and not a hemorrhagic stroke.

17.8.6.2 Hemorrhagic Stroke

Hemorrhagic stroke is defined as an acute episode of focal or global cerebral or spinal dysfunction caused by intraparenchymal, intraventricular, or subarachnoid hemorrhage.

17.8.6.3 Undetermined Stroke

Undetermined stroke is defined as an acute episode of focal or global neurological dysfunction caused by presumed brain, spinal cord, or retinal vascular injury as a result of hemorrhage or infarction but with insufficient information to allow categorization as either ischemic or hemorrhagic.

17.8.6.4 Stroke Disability

Disability should be measured by a reliable and valid scale in all cases, typically at each visit and at 60 days post randomization. For example, the modified Rankin Scale may be used to address this requirement

Scale	Disability
0	No symptoms at all
1	No significant disability despite symptoms; able to carry out all usual duties and activities
2	Slight disability; unable to carry out all previous activities, but able to look after own affairs without assistance
3	Moderate disability; requiring some help, but able to walk without assistance
4	Moderately severe disability; unable to walk without assistance and unable to attend to own bodily needs without assistance
5	Severe disability; bedridden, incontinent and requiring constant nursing care and attention
6	Dead

17.10 Cannabidiol and Drug-Drug Interactions for Patients with COVID-19

Notes:

1. Cannabidiol is a strong inhibitor of a number of CYP and UGT isoforms. Medications that depend on one (or more) of these enzyme isoforms for metabolism (that is, medications serve as a substrate for the enzyme) may then have slowed metabolism, thereby resulting in increased blood levels of the drug. For some drugs (particularly those with a narrow therapeutic index), this may result in toxicity.
2. The drugs listed are those that serve as a substrate for one or more of CYP2C8, CYP2C9, CYP2C19, CYP1A2, CYP2B6, UGT1A9 and UGT2B7.
3. Please note that certain drugs that are substrates for these enzymes are also strong inducers of CYP3A4 and therefore are exclusion criteria for this study, as depicted in **Appendix 17.7**.
4. Drugs listed in the table are arranged as follows: cardiovascular drugs, diabetes care drugs and then other commonly used drugs (in alphabetical order). The CYP or UGT isoform for which the drugs serve as a substrate are listed in the final column.
5. Many drugs serve as a substrate for more than one CYP or UGT isoform. They have only been recorded once in the table.
6. Undoubtedly, this patient population will be taking a wide spectrum of medication. If a medication of interest is not included in this list, please refer to a respected website such as DrugBank (www.drugbank.ca) to determine likelihood of drug-drug interaction.

Drug Class	Drug Name	Signs/Monitoring/Mitigation Strategies	Enzyme
Cardiovascular Drugs			
Diuretic	Torasemide	May cause hypotension, hypokalemia, increased creatinine - Monitor body weight and renal function. Adjust dose accordingly	CYP2C8
	Triamterene	May cause hyperkalemia, hyponatremia, nausea and vomiting, diarrhea, kidney stones – monitor potassium, adjust dose or change to other diuretic	CYP1A2
Statin			
	Cerivastatin	May cause muscle breakdown, muscle pain, Monitor cholesterol level and review adverse effect profile - Adjust dose or substitute another agent	CYP2C8
	Atorvastatin		
	Fluvastatin		
	Imvastatin		
	Pitavastatin		
	Lovastatin		
	Rosuvastatin	As above. Rarely causes memory loss/confusion	CYP2C9
	Simvastatin	May cause muscle damage – adjust dose or substitute other medication	CYP2C19
Other Cholesterol lowering agents			
	Ezetimibe	Usually used in combination with a statin. May cause joint pain, muscle breakdown, diarrhea, increased upper respiratory tract infections –	UGT1A9

		monitor cholesterol, adjust dose or use another agent	
	Gemfibrozil	May cause angioedema, muscle breakdown, liver damage – monitor cholesterol, liver enzymes. Adjust dose or use another agent	UGT1A9
Anticoagulant	Warfarin	Monitor INR - Adjust dose if needed	CYP2C8
	Apixaban	An oral anticoagulant (NOAC) which is Xa inhibitor. Can cause bleeding – if bleeding not controlled, reverse with anti-Xa agent	CYP2C8
	Dabigitran	May cause bleeding, allergic reactions, gastritis – monitor clotting and adjust dose	UGT1A9
Anti-platelet	Clopidogrel	Bruising, bleeding – adjust dose	CYP2C9
	Cilostazol	May cause headache, dizziness or diarrhea – adjust dose or change medication	CYP2C19
Anti-arrhythmic	Amiodarone	Monitor QTc, Measure blood levels - adjust dose	CYP2C8
	Quinidine	Not used often. Prolongs QTc and can cause digoxin toxicity. Causes diarrhea, gastric upset, ringing in ears, liver toxicity, auto-immune responses – monitor carefully and either decrease dose or discontinue medication	CYP2C9
	Lidocaine	Blocks sodium channels. May cause bradycardia, drowsiness, tingling,	CYP1A2

		numbness – when used as anti-arrhythmic, dose can be carefully controlled	
	Mexilitine	Blocks sodium channels. May cause nausea, drowsiness, skin reactions – monitor CG, adjust dose	CYP1A2
	Propafenone	Blocks sodium channels. May cause hypersensitivity reactions, dizziness, GI upset and rarely agranulocytosis – monitor ECG, adjust dose or change to other agent	CYP1A2
	Disopyramide	Blocks sodium channels. May cause urinary retention, hypotension, worsening heart failure, aggravate glaucoma – monitor ECG, adjust dose or use another agent	CYP1A2
	Tocainide	Blocks sodium channels. May cause dizziness, nausea, paresthesia, tremor. DD interactions common – monitor ECG, reduce dose or change to another agent	CYP1A2
	Flecainide	Blocks sodium channels. May cause dizziness, fatigue, worsen HF – monitor ECG, adjust dose	CYP1A2
Calcium Channel Blocker	Verapamil	May cause headache, bradycardia, edema, constipation, worsening HF - Reduce dose as needed	CYP2C8
	Diltiazem		
	Nicardipine		
	Nifedipine	May cause edema, cough, hypotension – adjust dose or use another agent	CYP1A2
Angiotensin receptor blocker	Irbesartan	May cause hypotension, muscle pains, angioedema –	CYP2C8

		reduce dose/change medication	
	Candesartan	Can cause hypotension/volume depletion – adjust dose	CYP2C9
	Valsartan		
	Losartan		
Anti-anginal	Perhexiline	Perhexiline is a pFOX inhibitor used in some countries for severe angina. It has complex metabolism and difficult to use	CYP2B6
Beta Blockers	Carvedilol	Bradycardia, tiredness, bronchospasm – reduce dose or suspend	CYP2C9
	Timolol	Timolol may be used for glaucoma. Can cause tiredness, SOB, worsening of asthma – adjust dose or change to another medication	CYP2C19
	Propranolol		
	Betaxolol	May cause bradycardia, nausea, constipation, unpleasant dreams and increase severity of asthma – adjust dose or change to other agent.	CYP1A2
Anti-hypertensives	Doxazosin	Hypotension, drowsiness, priapism - adjust dose	CYP2C9
	Clonidine (Alpha-2 agonist)	May cause dry mouth, dizziness, drowsiness, arrhythmia, and even confusion – Adjust dose or change to another agent	CYP1A2
	Labetalol (Alpha & Beta adrenergic blocker)	Primarily used to treat hypertension. May cause hypotension, fatigue, dizziness, bronchospasm –	UGT1A9

Peripheral Arterial Disease	Pentoxifylline	monitor BP, adjust dose or change to other medication	
Pulmonary anti-hypertensive	Bosentan	May cause tachycardia, headache, dizziness, gastric upset – adjust dose or use another agent	CYP1A2
	Ambrisentan	Hypotension, headache, transaminase elevation, edema, anemia, pulmonary veno-occlusive disease – requires close monitoring of co-administered drugs for DD interactions.	CYP2C9
PD5 Inhibitor	Sildenafil	Used to treat primary pulmonary hypertension. It is teratogenic if taken during pregnancy. Has limited usage	UGT1A9
		Hypotension, tachycardia - Avoid nitrates, adjust dose or change to another agent	CYP2C9

Drugs for Diabetes Care

Hypoglycemic	Rosiglitizzone	Monitor blood sugar - Adjust dose if needed.	CYP2C8
	Tolbutamide	Hypersensitivity may occur with Tolbutamide	
	Troglitazone		
	Gliquidone		
	Glyburide	Hypoglycemia, gastric discomfort, nausea/vomiting – monitor blood sugar and adjust dose as needed	CYP2C9
	Gliclazide	Hypoglycemia, abdominal pain, transaminase elevation	CYP2C9

		– monitor blood glucose and adjust dose.	
	Dapagliflozin	Improves glycemic control in Type 2 DM and improves HF management. May cause hypoglycemia, hypotension, rapid weight loss, dehydration, worsen urinary tract infections – monitor blood sugar, adjust dose	CYP1A2
	Empagliflozin	May cause dehydration, hypotension, hypoglycemia and increased urinary tract infection – monitor glucose and body weight and adjust dose	UGT1A9
Other Commonly Used Drugs			
Anti-asthmatic	Formoterol	A long acting B-2 agonist used for the control of asthma. May cause increased bronchospasm – monitor wheezing, adjust dose or change to short-acting product	UGT2B7
	Theophylline	May cause nausea, diarrhea, tachycardia, insomnia – reduce dose or change to other drug. Has lots of DD interactions	CYP1A2
Anti-convulsant	Phenytoin Trimethidione Carbamazepine	The taking of Phenytoin and Carbamazepine are listed exclusion criteria for this study (Appendix 17.7) Assess for excessive adverse effects such as drowsiness, swelling of	CYP2C8

		gums – Adjust dose or substitute other agent	
	Valproic Acid	Nausea and vomiting, drowsiness, dry mouth, transaminase elevations – monitor liver enzymes – adjust dose or change medication	CYP2C9
	Phenobarbital	The taking of Phenobarbital is a listed exclusion criteria for this study (Appendix 17.7)	CYP2C9
		Anti-seizure activity. Drowsiness, confusion – reduce dose or d/c	
Anti-diarrheal	Loperamide	May cause dehydration, weakness, faintness, rapid heart rhythm – discontinue if possible	CYP2C8
Anti-histamine	Loratadine	Can cause sleepiness, dry mouth, allergic reactions - Assess need for this medication during current illness	CYP2C19
Anti-depressant	Amitriptyline	May cause blurred vision, postural hypotension, dry mouth, constipation, urinary retention, suicidal thoughts - Reduce dose if appropriate.	CYP2C19
	Imipramine	Can cause dry mouth, drowsiness, hypotension, urinary retention and ECG changes – adjust dose or change med	CYP2C19
	Nortriptyline		
	Fluoxetine	May cause sleep disorder, sexual dysfunction, mania, suicidal behaviour – adjust dose or change med	CYP2C19
	Paroxetine		

Anti-inflammatory (Non-steroidal)	Diclofenac Ibuprofen Naproxen Celecoxib Ketorolac Meloxicam Valdecoxib	If taking long term, there may be abdominal discomfort, pain, nausea and increased risk of bleeding and renal damage - Should be discontinued if concern of toxicity. May cause GI bleeding – Discontinue if not required	CYP2C8 CYP2C9
Anti-inflammatory (Other)	Chloroquine Hydroxychloroquine	QT prolongation, nausea, vomiting, diarrhea, muscle twitching, Tinnitus/deafness – assess QT, adjust dose or discontinue drug	CYP2C8
	Phenylbutazone	Used mostly in animals recently. Can cause gastric irritation and bleeding and increase action of warfarin anti-coagulants – change to other anti-inflammatory	CYP2C9
	Indomethacin	Can cause edema, increased potassium, sodium, creatinine and hypertension – adjust dose or change medication	CYP2C19
Antipsychotic	Clozapine	May cause low WBC, drowsiness, increased salivation, hypotension, blurred vision, seizures and cardiac inflammation (myocarditis) – monitor WBC, ECG – reduce dose or chose another agent	CYP2C8
	Haloperidol	QT prolongation, tardive dyskinesia – adjust dose or use different medication	CYP2C9

Anti-viral	Remdesivir	Recently approved for use in COVID-19. May cause hypersensitivity reactions and increases in transaminases – slow infusion	CYP2C8
Anti-fibrotic	Pirfenidone	May cause nausea, GERD, skin rash, increased transaminases, dizziness, fatigue, weight loss – adjust dose or d/c during COVID-19 illness.	CYP1A2
Analgesic	acetaminophen	May cause liver damage if blood levels are too high for too long – reduce dose or use another analgesic	CYP1A2
Anxiolytic	Diazepam	May cause drowsiness, poor coordination, suicidal thoughts – reduce dose/change medication	CYP2C8
Sedatives/hypnotics	Zopiclone	Can cause depression, confusion, nightmares and even hallucinations - Dose should be adjusted or d/c if possible	CYP2C8
Cancer Therapeutics	Paclitaxil Cyclophosphamide	Assess for toxic effects such as platelet count - Consult with oncologist	CYP2C8
	Enzalutamide	The taking of Enzalutamide is a listed exclusion criteria for this study (Appendix 17.7)	CYP2C8
Hormone	Estradiol	May increase risk of venous thrombosis, heart attack, stroke - Should be discontinued if possible in prothrombotic state of COVID-19	CYP2C8

	Progesterone	Reduce dose	CYP2C9
Estrogen receptor modulator	Tamoxifen	Slight increase in risk of PE, stroke, uterine cancer. Causes hot flashes, weight loss – adjust dose or d/c	CYP2C9
Proton Pump Inhibitor	Pantoprazole	Allergic reactions, c difficile infection – adjust dose or change medication	CYP2C19
	Omeprazole	Nausea & vomiting, abdominal pain, C difficile infection – reduce dose/change medication	CYP2C8
H2 antagonist	Ranitidine	May cause headaches, bradycardia, liver damage, increase c difficile infection – adjust dose or change to other agent	CYP1A2
Serotonin 2C receptor Antagonist	Lorcaserin	Weight loss agent. Removed from USA market in 2020 due to increased cancer risk	CYP2B6
St John's Wort	
The taking of St John's Wort is a listed exclusion criteria for this study (Appendix 17.7)
 
May cause sleep disorder, anxiety, fatigue, dizziness, headaches – adjust dose or discontinue
		CYP2C19

